5.2.1.4 Dose Escalation Criteria

The molecular probe LS301 is an imaging agent binding to breast cancer cells and other malignant cells and will be visualized through by CVG which is a non-significant risk device. Similar to the FDA-approved agent ICG, we do not expect any serious adverse events caused by the agent.

A rolling six design will be used for the phase 1 portion. In the rolling six design, 2 to 6 patients can be enrolled to a dose each time. The dose de-escalation occurs when two or more DLTs occur at a dose level, while dose escalation occurs with 3/3, 4/4, 5/5, 5/6, or 6/6 patients are evaluated without DLT. (Refer to Section 8.1 for further details.)

5.2.2 Phase 2

After data from the phase 1 portion of the study have been submitted to and reviewed by the FDA, and if analysis of the data from phase 1 confirms the safety of administering LS301 in humans and establishes the optimal imaging dose, 88 patients will be enrolled in the phase 2 portion of the study after any necessary protocol revisions have been made based on phase 1 data and FDA approval.

It is expected that the study procedures for phase 2 will be the same as the procedures in phase 1. The optimal imaging dose of LS301 determined in phase 1 will be administered in phase 2.

The breast tissue and axillary LNs will be imaged non-invasively using the CVG and worn by a non-operating member of the surgical team. After removal of the breast cancer and SLNs using current best practice, a member of the surgical team who is not conducting the surgery will wear the CVG to determine if LS301 fluorescence is present at the margin and in SLNs, using a global threshold of 20% signal above background or a dynamic statistical threshold to indicate a positive margin. The accuracy of determining margin positivity will be established by comparing the CVG assessment to histopathology.

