5.2.4 Intraoperative Review

The operating surgeon will conduct breast cancer surgery as usual without using a device to visualize LS301 fluorescence. To prevent bias in data acquisition, a non-operating member of the study team will wear the CVG before the start of surgery to examine the breast tissue and axillary LNs non-invasively and at the completion of the surgery to examine the excised tissue, SLNs and surgical cavity. Findings with the study will be recorded but will not change the standard of care. The operating surgeon will remain blinded to the fluorescence images throughout the operation. The examining surgical team member will wear the CVG and image all six anatomical aspects (superior, inferior, anterior, posterior, medial and lateral) of the surgical specimen as well as the surgical cavity for LS301 fluorescence. The SPY system will be used for confirmatory fluorescence imaging and compared with CVG detection of LS301 fluorescence, during phase 2 of the study.

Detection of LS301 fluorescence at the cut edge of the excised specimen will determine margin positivity and presence of fluorescence in the SLNs indicate presence of metastatic cancer cells. Given that CVG can detect LS301 fluorescence in tumors several millimeters deep, investigators will use pathology data to initially train the system by correlating fluorescence intensity to background ratio with pathologist's margin assessment. The information will then be used in phase 2 to predict margin positivity in the OR. The detection of fluorescence on excised tissue without correlative fluorescence in the tumor cavity after lumpectomy will predict

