a negative margin for invasive ductal carcinoma. For DCIS, laser power modulation within the approved limit or dual excitation or emission method will be used to estimate the depth of fluorescence source. In general, a signal to background ratio of 1.2 (20% higher intensity than background) will be used as a global threshold to determine margin and SLN positivity status. In addition, a dynamic statistical thresholding approach will be used to delineate the boundary of tissue fluorescence. An intensity-based heat color map will be used for false color representation of the fluorescence to guide the examining surgeon. Areas with high LS301 accumulation, will be represented as red-hot compared to green and blue for surrounding tissue. A continuum of red fluorescence will indicate that the entire excised tissue is cancer. Fluorescence gradient using the heat color map showing red to blue from the edge of tumor tissue will indicate a positive margin. When the fluorescence emanating from tumors away from the margin (> 2 mm), hazy blue fluorescence will be observed at the surgical margin and will be classified as clear margin.

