5.4.2 Clinical Laboratory Testing

Laboratory tests will consist of the following: standard CBC, comprehensive metabolic panel and urinalysis obtained at the following time points:

- Baseline: within 30 minutes prior to injection of LS301
- 60 minutes after injection of LS301
- Approximately one hour prior to surgery

Approximately 14 ml of blood and a urine sample will be collected at each time point. For patients enrolled in phase 1B and phase 2 of the study, a portion of the blood samples from each time point will be used to identify the predominant blood protein(s) that binds LS301 and mediates the bioavailability of the agent (refer to Section 5.6). Phase 1B refers to phase 1 study after completing drug safety and selecting optimal dose for testing at 2 and 4 hours from injection to surgery. The current project is that if 3 patients at each of the 3 dose level do not experience adverse events, we will need only 9 patients for the drug safety study (phase 1A) and additional 9 patients at the selected dose for testing at 2, 4, and >12 hours (3 patients for each time point) from injection to surgery.

The results of standard of care laboratory testing obtained up to 30 days post injection will be reviewed. Analysis of this will take into account that the subject has undergone surgical removal of tumor and neoadjuvant treatment including hormonal therapy or chemotherapy.

The following changes from baseline clinical laboratory values are considered to be noteworthy and require assessment as to clinical significance when they fall outside of normal limits. Clinically significant changes in laboratory values should be followed up daily until they return to baseline or normal levels, or until follow-up is no longer warranted. Laboratory values that are abnormal at baseline but move into normal range will not be considered clinically significant. If a clinically significant change of a laboratory value is noted, it will be reported on the AE log.

Analyte	Change from baseline
Hemoglobin	> 2g/dL
WBCs	> 1 K/mm ³
Neutrophils	> 10 %
Lymphocytes	> 10%
Platelets	> 50 K/mm ³
Creatinine	> 0.75 mg/dL
BUN	> 20 mg/dL
Calcium	> 1mg/dL
Sodium	> 5 mmol/L
Potassium	> 0.5 mmol/L
CO ₂	> 4 mmol/L
ALT (SGPT)	> 150 IU/L
AST (SGOT)	> 100 IU/L
Alkaline Phosphatase	> 150 IU/L
Total Bilirubin	> 0.5 mg/dL
Albumin	> 1g/dL

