8.0 STATISTICAL CONSIDERATIONS

8.1 Study Design

A rolling six design which is intended for relatively safe trials and shortening the study duration is proposed for the phase 1 portion ⁷⁴. In the rolling six design, three to six patients can be enrolled to a dose each time. The dose de-escalation occurs when two or more DLT occur at a dose level while dose escalation occurs when 3/3, 4/4, 5/5, 5/6 or 6/6 patients are evaluated without DLT ⁷⁵. Three dose levels will be tested in the phase 1 study, 0.05, 0.075 and 0.10 mg/kg. LS301 will be administered intravenously at a starting dose of 0.05 mg/kg to a cohort of six patients and escalate/de-escalate following the decision rule of the rolling six design. Once six patients have been included at the current dose level, inclusions are suspended until at least five of the six patients have completed the procedure without DLT observed in the evaluation period. MTD is hit where two or more patients out of six at a dose level experience DLT. We do not expect any serious adverse events related to LS301 at the initial Dose Level 1. Once the MTD is determined, an expansion cohort with 9 patients will be tested at the MTD and an optimal imaging dose will be recommended for the subsequent phase 2 trial.

At the completion of the expansion cohort, a single arm phase 2 trial will be performed at the optimal imaging dose. A breast surgeon will perform breast conserving surgery per standard of care. At the completion of the surgery, a second investigator (to reduce bias in data collection) will wear the cancer vision goggle (CVG) to visualize the excised tissue to determine if there are any positive margins based on the presence of LS301 fluorescence. If any positive margins are observed, the subject will be considered to have a positive margin; otherwise, the margin is considered negative. The excised tissue will later be examined by a breast cancer pathologist. Standard pathologic techniques will be used to determine if there are positive margins. Particular attention will be paid to the sites marked following CVG assessment to confirm whether the margin is positive or negative at any of these sites, or positive at other locations not identified by CVG. No interventions will be allowed based on the CVG results.

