8.4 Sample Size

The sample size for the phase 1 part will depend on the observed DLT at each dose levels. The phase 1 expansion cohort will use 9 evaluable patients. The table below provides the probability of observing DLT in $\geq 33\%$ in 9 patients based on the binomial distribution. If the true DLT rate is as low as 5%, such a probability is small, only 0.0084 but if the true DLT is 50%, such a probability is very high at 0.91.

True DLT	probability of observed DLT $\geq 33\%$ in 9 patients
1%	0.000084
5%	0.0084
10%	0.053
20%	0.262
30%	0.537
40%	0.768
50%	0.91

The sample size for the phase 2 portion of the study was determined using the following calculations. A total of 88 (14 are expected to have positive margins after standard breast surgery) simultaneously achieves 84.7% power to detect an expected sensitivity of 0.95 against an unacceptable sensitivity of 0.7 and 100% power to detect an expected specificity 0.95 against an unfavorable specificity of 0.7 using a one-sided binomial test. The target significance level is 0.05. The actual significance level achieved by the test on sensitivity is 0.0475 and achieved by the test on specificity is 0.041. The current recall rate (i.e., margin positivity rate) after the use of cavity shave margin is ~19% ³⁶, which agrees with the best practices in Washington University, ~15.5%. 88 patients allows 92.66% power to test a reduction in positive margin rate from 15.5% to 5% based on a one-sided Binomial exact test at a 5% level.

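### The plan offers several rules for the phase 2 CVG margin call without naming the primary one or fixing it in time; the trained rule would rest on about two positive-margin patients.

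*Combined protocol and SAP*

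**What the plan says.** Section 5.2.4 describes training: "investigators will use pathology data to initially train the system by correlating fluorescence intensity to background ratio", set against the pathologist's reading of the margin. It continues: "The information will then be used in phase 2 to predict margin positivity in the OR". The words phase 1 do not appear there. But training that comes first and is then used in phase 2 is most naturally training on phase 1 patients.

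The same section also fixes a value in advance: "In general, a signal to background ratio of 1.2 (20% higher intensity than background) will be used as a global threshold". It adds a dynamic threshold alongside that value, and gives separate provisions for cavity fluorescence, DCIS and heat-map patterns. If the simple approach does not identify margins accurately, it turns to dual-wavelength depth profiling. It does not define what counts as failure.

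Section 5.2.2 (Phase 2) states the rule as an alternative: "using a global threshold of 20% signal above background or a dynamic statistical threshold to indicate a positive margin".

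The statistical section does not settle the matter. Section 8.1 bases a positive call on the presence of fluorescence, and 8.2.2 and 8.3.2 tabulate CVG calls against histopathology without stating a cut-off. No section gives a training rule, a number of training positives or a lock date.

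**The concern.** Sensitivity and specificity belong to one defined test. Here the index test could be any of four rules: the 1.2 ratio, the dynamic threshold, a trained rule or the dual-wavelength reading. Two separate problems follow.

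- **If the trained rule makes the call**, it has to be set from very few positive margins. A badly placed cut-off would then be carried into the 88 phase 2 patients and cost power.
- **If the rule is picked or changed once phase 2 pathology is known**, the reported rule is the one that did best on the same patients. The estimates are then too high, and the one-sided tests against 0.70 no longer hold their stated level.

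**Working it through.** **1. The plan's own figures (8.4).** 88 × 0.155 = 13.6, so 14 expected positives and 74 negatives.
- Sensitivity: reject 0.70 if at least 13 of 14 are detected. Exact level 0.0475, power at 0.95 = 0.847.
- Specificity: reject 0.70 if at least 59 of 74 are correct. Exact level 0.041, power above 0.999.

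Both reproduce the stated values.

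**2. Phase 1 patients at the phase 2 dose.** For escalation, 8.1 says "three to six patients can be enrolled to a dose each time". The expansion adds 9 (5.2.1, 5.4.2). Total: 3 + 9 = 12 to 6 + 9 = 15.

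**3. Expected positive margins = n × rate**, with rates from 8.4 (15.5%, 19%) and 1.11 (above 20%, taken as 20%):

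| Rate | n = 12 | n = 15 |
|---|---|---|
| 15.5% | 1.9 | 2.3 |
| 19% | 2.3 | 2.9 |
| 20% | 2.4 | 3.0 |

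At 15.5%, the binomial chance of no positives is 13% (n = 12) or 8% (n = 15). The chance of two or fewer is 72% or 58%.

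**4. Other readings of the documents, at 15.5%.**
- Section 5.4.2 describes "additional 9 patients at the selected dose for testing at 2, 4, and >12 hours (3 patients for each time point"), while 5.2.3 sets 4 to 24 hours from injection to surgery. Without the three 2-hour patients, 9 to 12 remain: 1.4 to 1.9 positives.
- Section 8.1 places the expansion at the MTD, and 5.2.1.2 allows the optimal dose to be lower. If the two differ, 3 to 6 patients remain: 0.5 to 0.9 positives.
- Pooling all three doses gives 3 × 3 + 9 = 18 to 3 × 6 + 9 = 27 patients: 2.8 to 4.2 positives.

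**5. What two positives can fix (illustration; the plan states no training rule).** Suppose the cut-off is the lowest ratio among m independent training positives. Its true sensitivity then follows Beta(m, 1). For m = 2 the mean is 2/3 = 0.67, the 5th percentile is √0.05 = 0.22 and the 95th is √0.95 = 0.97.

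**6. Cost of a poorly placed cut-off.** Power for at least 13 of 14 is 14p¹³(1 − p) + p¹⁴.
- p = 0.95: 85%
- p = 0.90: 58%
- p = 0.85: 36%

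**7. Cost of choosing the rule after pathology.** The exact level of 0.0475 leaves 0.05 − 0.0475 = 0.0025 to spare. Suppose two rules each have true sensitivity 0.70 and the better one is reported. The chance of a false success on sensitivity lies between 0.0475 (identical calls) and 2 × 0.0475 = 0.095. With independent calls it is 1 − 0.9525² = 0.093. For three rules the independent case gives 1 − 0.9525³ = 0.136. Rules read from the same images are correlated, so the true figure would fall between these limits.

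**The case against.** **The 1.2 ratio is pre-set.** It appears in both 5.2.2 and 5.2.4 and does not depend on how many phase 1 margins are positive. This stands. A reader might infer that the phase 2 cut-off as a whole is close to arbitrary, or rests on one or two specimens. The documents do not support that, because nothing says training replaces 1.2. Nothing says it does not, either. 1.2 applies only in general, has a stated alternative, and sits beside training whose output is to be used in phase 2.

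**There is more information than two positives.** The 10 to 13 expected negative patients, six imaged aspects per specimen, at least four specimens per patient and the breadloafed slices all inform the ratio. This also stands, mainly for specificity. The readings are clustered within patients and add no positive-margin patients.

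**The planning values do not depend on training.** Correct: 0.95 and 0.70 are design alternatives. Nor does the exact interval for two detected out of two (16% to 100%) measure movement of the cut-off; it describes estimation of sensitivity.

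**A locked rule is tested in fresh patients, and the OR call precedes pathology.** A rule fixed before phase 2 would show a poor cut-off as poor accuracy, not as bias. The bias therefore arises only if the reported rule is chosen or switched in light of phase 2 pathology. The plan does not exclude this: several readings are taken, and the dual-wavelength switch is triggered by the accuracy of the simple approach.

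**Protocol revisions before phase 2 are foreseen (5.2.2).** They are a suitable place for the fix, but the plan does not commit to making it.

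**Conclusion.** The point holds as an unnamed primary rule with no lock date. It does not show that the cut-off is arbitrary.

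If the trained rule makes the call, its sensitivity side rests on about two positive-margin patients at the phase 2 dose (1.9 to 2.3 at 15.5%). The documents' other readings run from about 0.5 to 4. A cut-off misplaced enough to lower true sensitivity to 0.90 would reduce power from 85% to 58%.

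If the rule is selected on phase 2 pathology, sensitivity and specificity are overstated. With two candidate rules, the false-success rate for sensitivity alone could approach twice its stated 0.0475.

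These figures assume that phase 1 patients have the same positive-margin rate as that planned for phase 2, that patients are independent, and that training uses phase 1 data. The last is an inference from 5.2.4. The Beta calculation illustrates one simple training rule only.

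**What to change.** - Name the 1.2 ratio as the single primary rule for the phase 2 margin call, in 5.2.2, 5.2.4 and 8.3.2 alike. State whether the cavity, DCIS and heat-map provisions modify that call.
- Allow 1.2 to be replaced only by another single value, chosen from phase 1 data by a criterion written down beforehand and locked before the first phase 2 patient. One possible criterion is that the interval for the fitted ratio, at the distance defining a positive margin, excludes 1.2. With so few positives that interval may be wide, in which case 1.2 stands.
- Do any phase 1 training on the continuous ratio against tumour-to-edge distance in mm, with patient as the cluster and the interval reported, rather than on the positive/negative call.
- Report the dynamic threshold and dual-wavelength readings as secondary.
- Reconcile the passages on the expansion dose (5.2.1 and 5.4.2 against 8.1) and on the 2-hour time point against the 4 to 24 hour window (5.4.2 against 5.2.3). They determine which patients can be used for training.

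The cost is one clustered regression and distance measurements on phase 1 specimens. The documents do not confirm that distance is recorded for each face, so this may be new pathology work. No extra patients are needed.

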5.3 Evaluability

All patients who receive an LS301 injection are evaluable for toxicity. Patients are evaluated from time of injection to one-hour post-injection.

Patients enrolled in phase 1 are evaluable for DLT assessment during the hour after injection. Patients in phase 2 will not be assessed for DLT.

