5.2.1.2 Definition of Optimal Dose

The optimal dose will be the dose at which fewer than 2 DLTs are observed and optimal image quality is observed. It need not be the maximum tolerated dose if optimal image quality is observed at a lower dose than the MTD.

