6.2 Sponsor-Investigator Reporting Requirements – UT Southwestern

Phase 1B and Phase 2:

6.2.1 Reporting to the Human Research Protection Program office (HRPP) at UT Southwestern Medical Center

Reporting will be conducted in accordance with UT Southwestern Medical Center IRB Policies.

Pre-approval of all protocol exceptions must be obtained prior to implementing the change.

6.2.2 Reporting to the Data and Safety Monitoring Committee (DSMC) at UT Southwestern Medical Center

For local patients, in addition to the sponsor monitoring, the Simmons Comprehensive Cancer Data Safety and Monitoring Committee (DSMC) will be monitoring only local unanticipated SAE's as reported to the IRB. The chair will review only local unanticipated SAE's in real time. These are then reviewed quarterly at DSMC meetings. The chairman of the DSMC is responsible for this ongoing monitoring. Monitoring of serious adverse events happens by the DSMC chairman in real time and an annual review takes place to look at trends in adverse events, accrual and other applicable study events. The Principal Investigator (or a designated co-investigator) will be primarily responsible for monitoring study accrual rate, study attrition/withdrawals/dropouts, patterns of adverse events and/or unanticipated event and patterns of protocol violations and/or deviations at this site.

Trial monitoring will be conducted no less than annually and refers to a regular interval review of trial related activity and documentation which includes but is not limited to accuracy of case report forms, protocol compliance, timeliness and accuracy of Velos entries and AE/SAE management and reporting. Documentation of trial monitoring will be maintained along with other protocol related documents and will be reviewed during internal audit.

The Sponsor Investigator (or designee) is required to notify DSMC of any unanticipated problems involving risks to participants or others occurring at UTSW that have been reported to and acknowledged by HRPP. (Unanticipated problems reported to HRPP and withdrawn during the review process need not be reported to DSMC.)

DSMC must be notified in real-time as they are reported to the IRB to the UTSW Simmons Cancer Center DSMC Coordinator.

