6.2.3 Reporting to the FDA

The conduct of the study will comply with all FDA safety reporting requirements. **PLEASE NOTE THAT REPORTING REQUIREMENTS FOR THE FDA DIFFER FROM REPORTING REQUIREMENTS FOR HRPP/DSMC.** It is the responsibility of the investigator to report any unanticipated problem to the FDA as follows:

- Report any unexpected fatal or life-threatening suspected adverse reaction (refer to Appendix A for definitions) no later than **7 calendar days** after initial receipt of the information.
- Report a suspected adverse reaction that is both serious and unexpected (SUSAR, refer to Appendix A), no later than **15 calendar days** after it is determined that the information qualifies for reporting. Report an adverse event (refer to Appendix A) as a suspected adverse reaction only if there is evidence to suggest a causal relationship between the drug and the adverse event, such as:
 - A single occurrence of an event that is uncommon and known to be strongly associated with drug exposure
 - One or more occurrences of an event that is not commonly associated with drug exposure but is otherwise uncommon in the population exposed to the drug
 - An aggregate analysis of specific events observed in a clinical trial that indicates those events occur more frequently in the drug treatment group than in a concurrent or historical control group
- Report any findings from epidemiological studies, pooled analysis of multiple studies, or clinical studies that suggest a significant risk in humans exposed to the drug no later than **15 calendar days** after it is determined that the information qualifies for reporting.
- Report any findings from animal or in vitro testing that suggest significant risk in humans exposed to the drug no later than 15 calendar days after it is determined that the information qualifies for reporting.
- Report any clinically important increase in the rate of a serious suspected adverse reaction of that listed in the protocol or IB within 15 calendar days after it is determined that the information qualifies for reporting.

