7.2 Phase 1B and Phase 2: UTSW

In compliance with the Simmons Cancer Center Data and Safety Monitoring Committee, the Principal Investigator will provide a Data and Safety Monitoring (DSM) report to the Simmons Cancer Center Data and Safety Monitoring Committee (DSMC) semi-annually beginning six months after accrual has opened (if at least one patient has been enrolled) or one year after accrual has opened (if no patients have been enrolled at the six-month mark).

The Principal Investigator will review all patient data at least every 6 months, and provide a semi-annual report to the DSMC. This report will include:

- HRPP protocol number, protocol title, Principal Investigator name, data coordinator name, regulatory coordinator name, and statistician name
- Date of initial HRPP approval, date of most recent consent HRPP approval/revision, date of HRPP expiration, date of most recent QA audit, study status, and phase of study
- History of study including summary of substantive amendments; summary of accrual suspensions including start/stop dates and reason; and summary of protocol exceptions, error, or breach of confidentiality including start/stop dates and reason
- Study-wide target accrual and study-wide actual accrual
- Protocol activation date
- Average rate of accrual observed in year 1, year 2, and subsequent years
- Expected accrual end date and accrual by cohort
- Objectives of protocol with supporting data and list the number of participants who have met each objective
- Early stopping rules with supporting data and list the number of participants who have met the early stopping rules

- Summary of toxicities separated by cohorts with the number of dose-limiting toxicities indicated
- Abstract submissions/publications
- Summary of any recent literature that may affect the safety or ethics of the study

The study principal investigator and Research Study Coordinator will monitor for serious toxicities on an ongoing basis. Once the principal investigator or Research Study Coordinator becomes aware of an adverse event, the AE will be reported to the HRPP and DSMC according to institutional guidelines.

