8.5 Early stopping rule

We don't expect any toxicities for LS301 but grade 1 toxicity is usually acceptable for imaging agent. As such, the trial will stop early in the phase 1 part following the rolling six design rule if dose level 1 has two out of six patients experience DLTs.

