Breach of confidentiality	Within 10 working days.				

Event	Expedited Reporting Timelines				
	HRPO – Washington University	HRPPO – UT Southwestern	QASMC – Washington University	DSMC – UT Southwestern	FDA
Incarceration	If withdrawing the participant poses a safety issue, report within 10 working days. If withdrawing the participant does not represent a safety issue and the patient will be withdrawn, report at continuing review.				

Event	Routine Reporting Timelines				
	HRPO – Washington University	HRPPO – UT Southwestern	QASMC – Washington University	DSMC – UT Southwestern	FDA
Adverse event or SAE that does not require expedited reporting	If they do not meet the definition of an unanticipated problem involving risks to participants or others, report summary information at the time of continuing review	Adverse events will be reported at Continuing Review.	Adverse events will be reported in the toxicity table in the DSM report which is typically due every 6 months.	Adverse events will be reviewed at Annual DSMC Review	The most current toxicity table from the DSM report is provided to the FDA with the IND's annual report.
Minor deviation	Report summary information at the time of continuing review.	Minor deviations will be reported at Continuing Review.		Minor deviations will be reviewed at Annual DSMC Review	

Complaints	If the complaint reveals an unanticipated problem involving risks to participants or others OR noncompliance, report within 10 working days. If the event results in the death of a participant enrolled at WU/BJH/SLCH, report within 1 working day. Otherwise, report at the time of continuing review.	All complaints are summarized in the next progress report submitted as part of continuation review or in the final report submitted to inactivate the study			
Incarceration	If withdrawing the participant poses a safety issue, report within 10 working days. If withdrawing the participant does not represent a safety issue and the patient will be withdrawn, report at continuing review.				

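### Phase 2 (88 patients) has no prespecified toxicity count that triggers a pause; one can be added from data already collected, in the revision foreseen before phase 2

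*Combined protocol and SAP*

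**What the plan says.** **Phase 2.** A DLT is a grade 2 or higher toxicity in the hour after injection that is at least possibly related to LS301 (5.2.1.3). Section 5.3 makes everyone who is injected evaluable for toxicity over that same hour, but adds "Patients in phase 2 will not be assessed for DLT". Section 8.5 has the only early stopping rule: "the trial will stop early in the phase 1 part following the rolling six design rule if dose level 1" has two DLTs in six patients. Section 8.2.2 names toxicity as the phase 2 secondary endpoint and gives no threshold.

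**Monitoring.** Section 7.2, which covers phases 1B and 2 together, requires a semi-annual DSMC report containing "Summary of toxicities separated by cohorts with the number of dose-limiting toxicities indicated" and "Early stopping rules with supporting data and list the number of participants who have met the early stopping rules". Section 6.2.2 says "Monitoring of serious adverse events happens by the DSMC chairman in real time and an annual review takes place", asks the principal investigator to watch patterns of adverse events, and sends unanticipated problems to the DSMC as they go to the IRB (within 5 business days in Appendix B). For events outside expedited reporting, Appendix B says "Adverse events will be reviewed at Annual DSMC Review". The FDA rule in 6.2.3 is to "Report any clinically important increase in the rate of a serious suspected adverse reaction".

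**Phase 1B.** Section 5.2.1.2 says "The optimal dose will be the dose at which fewer than 2 DLTs are observed and optimal image quality is observed", with no denominator. Section 5.2.1.4 de-escalates at two or more DLTs at a dose level. Section 8.1 also words the rule as two of six. Section 8.4 tabulates the chance of DLTs in at least 33% of 9 patients and attaches no action.

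**The concern.** The protocol's own standard for this imaging agent is strict. Section 8.5 treats grade 1 toxicity as acceptable, and two related grade 2 reactions in six patients stop the trial at dose level 1. Participants get no offsetting benefit, because the images may not alter surgery. Yet once the largest group starts, the same events carry no agreed consequence. The real-time review by the DSMC chair and the FDA rate-increase rule both concern serious events. A related grade 2 reaction that is neither serious nor judged an unanticipated problem reaches the DSMC mainly through periodic review. If such reactions accumulate, whether to pause would be decided ad hoc, after the data are seen. The two 7.2 report items also have nothing to count in phase 2.

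**Working it through.** All toxicity rates below are assumptions; the documents give none for humans. X is the number of patients with an event meeting 5.2.1.3, at true rate p.

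**1. The plan's own table (8.4).** P(X ≥ 3 | 9, p) gives 0.0084, 0.053, 0.262, 0.537, 0.768 and 0.910 at p = 5%, 10%, 20%, 30%, 40% and 50%, as stated. The 1% row computes to 0.000080 against 0.000084, which is immaterial. No figure in the plan concerns a phase 2 toxicity rule.

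**2. Share of exposure.** With three dose levels, 9 expansion patients and 88 in phase 2:
- six per dose: 88/(18 + 9 + 88) = 0.765
- three per dose, as 5.4.2 projects: 88/(9 + 9 + 88) = 0.830

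**3. What a clean phase 1 rules out.** With zero DLTs at the chosen dose, the one-sided 95% upper limit is 1 − 0.05^(1/15) = 0.181 (6 + 9 patients) or 1 − 0.05^(1/12) = 0.221 (3 + 9).

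**4. Chance that a dose with a true 20% rate passes phase 1.**
- Phase 1A, six patients, at most one DLT: 0.8^6 + 6(0.2)(0.8^5) = 0.655
- Phase 1A, three patients, expanded to six after one DLT: 0.8^3 + 3(0.2)(0.8^2)(0.8^3) = 0.512 + 0.197 = 0.709
- Phase 1B, at most one DLT in 9: 0.8^9 + 9(0.2)(0.8^8) = 0.134 + 0.302 = 0.436
- Both, 1B counted alone: 0.655 × 0.436 = 0.286, or 0.709 × 0.436 = 0.309
- Both, DLTs pooled at the dose: P(X ≤ 1 | 15) = 0.167, or 0.512 × 0.436 + 0.197 × 0.134 = 0.250

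At a true 30% the same steps give 0.420–0.494 (1A only), 0.082–0.097 (1B alone added) and 0.035–0.073 (pooled). FDA review is not modelled.

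**5. A phase 2 boundary.** At n = 11, 22, …, 77, take the smallest r with P(X ≥ r | n, 0.10) ≤ 0.02. This gives r = 4, 6, 8, 10, 11, 13, 14, with tails 0.0185, 0.0182, 0.0141, 0.0103, 0.0189, 0.0128 and 0.0197.

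Pause probabilities come from exact recursion. Carry forward the distribution of counts still below the boundary, add Binomial(11, p) at each look, and remove the mass at or above r. At p = 0.20 the mass removed is 0.161, 0.145, 0.104, 0.077, 0.128, 0.056 and 0.085, which sums to 0.757 before rounding. Mean enrolled is the sum of n times the mass removed at each look, plus 88 × 0.243, which is 50.5.

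| True rate | P(pause) | Mean enrolled | Expected events, no rule (88p) | Expected events if enrolment ended at the pause (p × mean) |
|---|---|---|---|---|
| 10% | 0.056 | 85.0 | 8.8 | 8.5 |
| 20% | 0.757 | 50.5 | 17.6 | 10.1 |
| 30% | 0.995 | 23.4 | 26.4 | 7.0 |

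**6. Dependence on the acceptable rate.** Same construction, same 0.02 cut-off:
- 5% acceptable (3, 5, 6, 7, 7, 8, 9): pauses 4% at a true 5% and 99% at 20%
- 15% acceptable (5, 8, 10, 13, 15, 17, 19): pauses 5% at a true 15%, 27% at 20% and 90% at 30%

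**7. Phase 1B readings.** Two of 9 triggers with probability 0.225, 0.564 and 0.804 at true rates of 10%, 20% and 30%. Three of 9 triggers with probability 0.053, 0.262 and 0.537. If one phase 1A DLT at that dose already counts, a single 1B event reaches two: 1 − 0.8^9 = 0.866 at 20%.

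**The case against.** The strongest reply is that phase 2 is already protected and its text is provisional. Phase 2 opens only if phase 1 confirms safety, and after FDA review and any needed revisions (5.2.2). Unanticipated problems go to the DSMC promptly whether or not they are serious. Section 7.2 also sends adverse events to the DSMC under institutional guidelines, and 5.9 lets the institution close the study. Since 8.5 expects no toxicity, a cluster of related grade 2 reactions might well qualify as an unanticipated problem. Nothing in the documents suggests a rate of 20% or 30%, and the pause probabilities depend heavily on the acceptable rate chosen.

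Much of this stands, and it limits the point. A reader might infer that phase 2 has no safety monitoring, or that non-serious reactions can reach the DSMC only through periodic reports; the routes just listed rule out both. A reader might also infer that 7.2 contradicts 5.3. But 7.2 covers phase 1B, where DLT counts are meaningful, its list nearly repeats the phase 1A list in 7.1, and for phase 2 the items could read as not applicable. Nor is phase 1B without a rule: 5.2.1.2, 5.2.1.4 and 5.3 together most naturally carry the two-DLT limit over.

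What the reply does not supply is a count that obliges anyone to pause during phase 2. FDA review is a gate before enrolment, and the other routes rest on case-by-case judgement.

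**Conclusion.** The gap is real but specific: a missing prespecified trigger in phase 2, not missing surveillance. It affects 77% to 83% of planned injections, at a point where even a clean phase 1 leaves rates up to 18% or 22% compatible with the data. With the two-DLT rule applied in 1B, a dose with a true 20% rate would still pass phase 1 between 17% and 31% of the time (4% to 10% at a true 30%), before any FDA judgement. The 76% and 99.5% pause probabilities are conditional on such a dose reaching phase 2 and on a 10% acceptable rate; neither is evidence that LS301 is that toxic. The change is worth making because it replaces a stated exemption with a rule that uses data already collected. The phase 1B wording is a minor clarification and would not merit an amendment on its own.

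**What to change.** Make these changes in the revision that 5.2.2 foresees before phase 2:

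- **5.3:** replace the exemption with a statement that events meeting 5.2.1.3 are counted in phase 2 for safety monitoring, not for dose decisions.
- **8.5:** add a pause and DSMC review at 4/11, 6/22, 8/33, 10/44, 11/55, 13/66 or 14/77, with the 10% acceptable rate confirmed or reset by the sponsor from phase 1 data. A boundary starting at 5 of 11 is too lax: it continues at 4/11 (36%), above the 2/6 (33%) that stops phase 1 at dose level 1. Acting as soon as a count is reached within its block leaves the pause probabilities unchanged, because counts cannot fall, and can only reduce enrolment before a pause.
- **6.2.2:** keep the real-time review as the route for a single severe reaction.
- **7.2:** report these counts under the two existing items.
- **Phase 1B (minor):** one sentence in 8.5 confirming that fewer than two DLTs at a dose level covers the 9 expansion patients, and saying whether phase 1A DLTs at that dose count.

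The cost is amendment wording and seven counts from the Toxicity Form, with no new patient assessments. The downside is a 5.6% chance of an unneeded phase 2 pause at a true 10% rate. Confirming the two-DLT rule on the 9 patients alone means it triggers 23% of the time at a true 10%.
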